9.2. Sample Size Determination

A sufficient number of participants will be screened to achieve approximately 40 participants (approximately 27 participants in the PF-06946860 200 mg Q3W arm and 13 participants in the placebo arm) randomly assigned to study intervention in approximately a 2:1 ratio. This is expected to ensure completion of Part A of the study of approximately 30 evaluable participants (approximately 20 PF-06946860: 10 placebo), assuming a discontinuation rate of 25%. There is no required sample size for Part B of the study.

The study sample size has been chosen to provide sufficient data for an initial assessment of efficacy in the population for facilitating internal decision making and may be used for future study planning. Completion of 30 participants, with a 2:1 ratio, gives acceptable Operating Characteristics in that:

- The probability of achieving statistical significance (at the 5% significance level, using a 1-sided t-test) for a true effect of 4 versus placebo for the patient reported 7-day recall Cancer-Related Cachexia Symptom Assessment-Appetite score (ranging 0-10) at 4 weeks is approximately 80%.
- An observed effect of 2.7 versus placebo for the patient reported 7-day recall Cancer-Related Cachexia Symptom Assessment-Appetite score at 4 weeks should achieve statistical significance (at the 5% significance level, using a 1-sided test).

A conservative estimate of the between-subject standard deviation for the change from baseline in the patient reported 7-day recall Cancer-Related Cachexia Symptom Assessment-Appetite score of 4.2 has been used. This estimate was based on the observed variability of a similar appetite scale in a double-blind controlled clinical trial assessing the effect of megestrol acetate on appetite in patients with far-advanced cancer.³²

Evaluable participants are defined as in [Section 9.3](#).

Participants who withdraw from the study will not be replaced.

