9.4.1.1. Analyses for Continuous Endpoints

The mixed effects repeated measures (MMRM) model will include participant as a random term, and baseline, time (as a factor), baseline-by-time interaction, treatment and treatment-by-time interaction as fixed terms in the model. An unstructured covariance matrix will be fitted to the repeated times within subject (other covariance matrices will be considered if necessary), and the Kenward-Roger approximation will be used for estimating degrees of freedom. Additional terms may be fitted in the model (eg, cancer type, PROMIS-Pain 1a change from baseline score), as appropriate.

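### Protocol 9.2 names a one-sided t-test, but its 80% power and 2.7-point threshold are normal-approximation values; the t-test gives about 77% and 2.8

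*Protocol*

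**What the plan says.** Protocol Section 9.2 plans about 40 randomized participants. With 25% discontinuation, about 30 should complete Part A, split roughly 20 on PF-06946860 and 10 on placebo. It then states: "Completion of 30 participants, with a 2:1 ratio, gives acceptable Operating Characteristics". Two bullets support this.

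- The first gives the probability of significance "at the 5% significance level, using a 1-sided t-test) for a true effect of 4 versus placebo" on the appetite score, "ranging 0-10) at 4 weeks is approximately 80"%.
- The second reads "An observed effect of 2.7 versus placebo for the patient reported 7-day recall" appetite score at 4 weeks "should achieve statistical significance (at the 5% significance level, using a 1-sided test").

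The section takes the between-subject SD of the change from baseline as 4.2 and calls it conservative.

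For the analysis itself, Protocol 9.4.1.1 and SAP 5.2.3 specify a repeated-measures mixed model in which "the Kenward-Roger approximation will be used for estimating degrees of freedom". Protocol 9.4.2 reports the Week 4 difference with a 90% CI. SAP 5.1 plans no formal hypothesis tests and no decision rules.

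**The concern.** The power bullet names a t-test. With about 30 completers the t critical value is noticeably larger than the normal one, so it matters which was used. The stated figures look as if the normal value was used under a t-test label. These are the only two figures that Section 9.2 offers for calling 30 completers acceptable, and running the named test on the stated inputs reproduces neither.

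The threshold is the more concrete of the two. Someone making an internal decision could take 2.7 as the mark of success, although at the planning SD a t-based 90% CI around an observed 2.7 would still include zero.

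**Working it through.** **Inputs, all from Protocol 9.2:** 20 active and 10 placebo completers; SD 4.2; true difference 4; one-sided 5% level. An equal-variance two-sample comparison has 20 + 10 − 2 = 28 degrees of freedom.

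**Standard error:** SE = 4.2 × √(1/20 + 1/10) = 4.2 × √0.15 = 1.627. The standardized true effect is 4/1.627 = 2.459.

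**Reproducing the plan's figures with the normal approximation** (critical value 1.645)
- Smallest significant difference: 1.645 × 1.627 = 2.68, which prints as 2.7.
- Power: Φ(2.459 − 1.645) = 79.2%, which fits approximately 80%.

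**The t-test that the text names** (critical value t(0.95, 28) = 1.701)
- Smallest significant difference: 1.701 × 1.627 = 2.77, which prints as 2.8.
- Power from the noncentral t with noncentrality 2.459: 77.5% (0.7746).

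**An observed difference at the planning SD**

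| Observed difference | Statistic | One-sided p, t on 28 df | One-sided p, z |
|---|---|---|---|
| 2.7 | 2.7/1.627 = 1.660 | 0.054 | 0.048 |
| 2.8 | 2.8/1.627 = 1.721 | 0.048 | 0.043 |

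**Size of the gap:** the stated 80% is 2.5 points above the t-test power. Of this, 1.8 points (79.2 against 77.5, from unrounded values) come from z in place of t, and 0.8 points from rounding 79.2% up to 80%. The threshold is 0.07 too low (2.77 − 2.70).

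**Sensitivity of the t-test result to the inputs**

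| Completers | SD | Smallest significant difference | Power at 4 |
|---|---|---|---|
| 20:10 | 4.20 | 2.77 | 77.5% |
| 20:10 | 4.15 | 2.73 | 78.3% |
| 20:10 | 4.10 | 2.70 | 79.2% |
| 21:10 | 4.20 | 2.74 | 78.1% |
| 20:11 | 4.20 | 2.68 | 79.7% |
| 21:9 | 4.20 | 2.85 | 75.4% |

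The t-test comes close to both printed figures only with 20:11 or an SD of 4.10. Section 9.2 states neither: 20:11 is 31 completers and not 2:1, and 4.10 does not round to 4.2.

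**The case against.** The best defence is that the printed inputs are rounded.

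- **Rounding of the inputs.** An SD between 4.15 and about 4.174 also prints as 4.2, and the split is only approximate. At SD 4.15, or with 21:10, the t-test threshold is 2.73 or 2.74, which prints as 2.7, with power of about 78%. So the use of a normal approximation is inferred, not documented. This does not rescue the second bullet, however: in both cases an observed 2.7 still falls below the threshold (one-sided p = 0.052).
- **The word approximately.** It softens the power figure, and the normal approximation does not reach 80% either. This stands in part, and it makes the threshold the firmer error. The threshold carries no such qualifier.
- **The second bullet says only "at the 5% significance level, using a 1-sided test".** Taken alone, 2.7 is right for a z-test. But both bullets describe the same 30 completers, and the one above names the t-test. If a z-test was meant, the two bullets use different tests without saying so, which also needs correcting. No section plans an analysis with a z reference distribution.
- **Baseline adjustment.** The planned model adjusts for baseline, which could reduce the residual SD. As an assumption, a correlation of 0.2 to 0.3 between baseline and change would give t-based thresholds of about 2.71 to 2.64 and power of about 79% to 81%. The planned analysis may therefore do no worse than the printed figures. But Section 9.2 presents them as the result of a t-test with SD 4.2 and claims no such gain.
- **No formal test is planned.** This is true and limits the consequence. It does not make the figures correct.

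**Conclusion.** The point holds and is minor. At 20:10 completers and SD 4.2, the one-sided 5% t-test gives 77.5% power for a true difference of 4 and needs an observed difference of 2.77. The stated 80% and 2.7 are the normal-approximation values, rounded.

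This rests on taking the inputs of Section 9.2 at face value with an equal-variance t-test. The statement that an observed 2.7 is not significant also assumes that the observed SD equals the planning SD. That the two figures came from a normal formula is the natural explanation, since both fit it, but the text does not say so. The estimates and intervals that will be reported do not use either figure.

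**What to change.** In Protocol 9.2, change the power in the first bullet to approximately 77%. In the second bullet, change the observed effect to 2.8 and name a one-sided t-test, so that both bullets refer to the same test.

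Stating openly that a normal approximation was used would also remove the mismatch. The t figures are preferable because the planned intervals are t-based.

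The cost is a text edit and two slightly less favourable figures. The sample size, conduct and analysis do not change.

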9.3. Analysis Sets

For purposes of analysis, the following analysis sets are defined:

Participant Analysis Set	Description
Enrolled/Randomly assigned to study intervention	"Enrolled" means a participant's, or their legally authorized representative's, agreement to participate in a clinical study following completion of the informed consent process. Potential participants who are screened for the purpose of determining eligibility for the study, but do not participate in the study, are not considered enrolled, unless otherwise specified by the protocol.
Evaluable	All participants randomly assigned to study intervention and who take at least 1 dose of study intervention. Participants will be analyzed according to the randomized study intervention.
Safety	All participants randomly assigned to study intervention and who take at least 1 dose of study intervention. Participants will be analyzed according to the product they actually received.

Defined Analysis Set	Description
Censored	For participants who discontinue study intervention, receive prohibited medication and/or miss a dose, all observations post-discontinuation, post-medication or post-missed dose will be censored and treated as missing data.
PK	All participants randomly assigned to study intervention and who take at least 1 dose of PF-06946860 and in whom at least 1 PK concentration value is reported.
PD	All participants randomly assigned to study intervention and who take at least 1 dose of study intervention and in whom at least 1 PD (GDF-15) concentration value is reported.
Immunogenicity	All participants randomly assigned to study intervention and who take at least 1 dose of PF-06946860 and in whom at least 1 ADA result is reported.

9.4. Statistical Analyses

The SAP will be developed and finalized before any analyses are performed and will describe the analyses and procedures for accounting for missing, unused, and spurious data. This section is a summary of the planned statistical analyses of the primary and secondary endpoints.

9.4.1. General Considerations

For objectives relating to Part A of the study, each treatment arm (PF-06946860 or placebo) will be reported separately through the 6-week double-blind treatment period only (including follow-up for any participants not continuing onto Part B of the study).

9.4.1.1. Analyses for Continuous Endpoints

The mixed effects repeated measures (MMRM) model will include participant as a random term, and baseline, time (as a factor), baseline-by-time interaction, treatment and treatment-by-time interaction as fixed terms in the model. An unstructured covariance matrix will be fitted to the repeated times within subject (other covariance matrices will be considered if necessary), and the Kenward-Roger approximation will be used for estimating degrees of freedom. Additional terms may be fitted in the model (eg, cancer type, PROMIS-Pain 1a change from baseline score), as appropriate.

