9.1. Estimands and Statistical Hypotheses

9.1.1. Estimands

*Estimand related to the **appetite** primary objective:*

Estimand 1 (similar to “hypothetical”) is intended to provide a population level estimate of the treatment effect on the change from baseline Appetite score for PF-06946860 compared to placebo in all evaluable participants under the scenario of no discontinuation of study intervention and without the potential confounding effects of prohibited medications, regardless of the participants’ compliance with dosing (ie, using the Censored analysis set).

- Population: Patients with advanced cancer, anorexia and elevated circulating GDF-15 levels.

- Variable: Change from baseline for the patient reported 7-day recall Cancer-Related Cachexia Symptom Assessment-Appetite score at Week 4.
- Intercurrent Events:
 - a. Discontinuation of study intervention - Data collected after a participant has discontinued study intervention will be censored and treated as missing data.
 - b. Prohibited medications - Data collected after a participant has received prohibited medications, that would modulate the primary endpoint, will be censored and treated as missing data. The list of concomitant medications will be reviewed prior to database lock to determine which would be classed as “prohibited” for this estimand.
 - c. Inadequate compliance - Data collected after a participant has missed a dose will be censored and treated as missing data.

Missing data due to censoring, study withdrawal or other reasons, are assumed to be missing at random.

- Population level summary: Difference in mean change from baseline for the patient reported 7-day recall Cancer-Related Cachexia Symptom Assessment-Appetite score at Week 4 between PF-06946860 and placebo.

This estimand will similarly be applied to the appetite secondary objective (ie, change from baseline at Weeks 1, 2, 3, 5 and 6).

Alternative estimands for the primary objective may be used in order to examine the robustness of the results and will be detailed in the SAP.

Estimand related to the fatigue secondary objective:

Estimand 2 will be similar to Estimand 1, except for the following:

- Variable: Change from baseline for the patient reported 7-day recall Cancer-Related Cachexia Symptom Assessment-Fatigue score at Weeks 1, 2, 3, 4, 5 and 6.

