9.4.2. Primary Endpoint(s)

Change from baseline for patient reported 7-day recall Cancer-Related Cachexia Symptom Assessment–Appetite score will be analyzed using Estimand 1 and an MMRM model (as per [Section 9.4.1.1](#)). The MMRM model will be fitted to the change from baseline at all post-treatment timepoints up to Week 6 using the *Censored* analysis set. Least squares means (and 90% CIs) and mean differences versus placebo (and 90% CIs), at Week 4, will be provided. No adjustments will be made for multiplicity.

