9.4.3. Secondary Endpoint(s)

Endpoint	Statistical Analysis Methods
Change from baseline for patient reported 7-day recall Cancer-Related Cachexia Symptom Assessment-Appetite score, at Weeks 1, 2, 3, 5 and 6.	Results related to this endpoint will be obtained from the Primary Analysis model above. Least squares means (and 90% CIs) and mean differences versus placebo (and 90% CIs), at each week, will be provided. No adjustments will be made for multiplicity.
Change from baseline for patient reported 7-day recall Cancer-Related Cachexia Symptom Assessment-Fatigue score, at Weeks 1, 2, 3, 4, 5 and 6.	Change from baseline for patient reported 7-day recall Cancer-Related Cachexia Symptom Assessment-Fatigue score will be analyzed using Estimand 2 and an MMRM model (as per Section 9.4.1.1). The MMRM model will be fitted to the change from baseline at all post-treatment timepoints up to Week 6 using the Censored analysis set. Least squares means (and 90% CIs) and mean differences versus placebo (and 90% CIs), at each weeks, will be provided. No adjustments will be made for multiplicity.
Incidence of adverse events and laboratory abnormalities, in Part A of the study.	All safety analyses will be performed on the safety population. The safety data will be summarized in accordance with Pfizer Data Standards. All safety data will be summarized descriptively through appropriate data tabulation, descriptive statistics, categorical summaries, and graphical presentations, as appropriate.

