### 5.2.3. Mixed Models Repeated Measures (MMRM) Analysis

*The mixed effects repeated measures (MMRM) model will include participant as a random term, and baseline, time (as a factor), baseline-by-time interaction, treatment and treatment-by-time interaction as fixed terms in the model. An unstructured covariance matrix will be fitted to the repeated times within subject (other covariance matrices will be considered if necessary, e.g. if convergence is not obtained or model fit is not adequate), and the Kenward-Roger approximation will be used for estimating degrees of freedom. Additional terms may be fitted in the model (e.g. cancer type, PROMIS-Pain 1a change from baseline score), as appropriate.*

Least-squares (LS) means (and 90% CIs) and mean differences versus placebo (and 90% CIs), at each timepoint, will be provided. Means and differences averaged over the timepoints may also be included. No adjustments will be made for multiplicity.

Example SAS code is provided in [Appendix 1](#).

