### 6.1. Primary Endpoint(s)

#### 6.1.1. Change from baseline for patient reported 7-day recall Cancer-Related Cachexia Symptom Assessment–Appetite score, at Week 4.

##### 6.1.1.1. Main Analysis

Absolute values and changes from baseline in the Cancer-Related Cachexia Symptom Assessment–Appetite score will be summarized descriptively by treatment group and timepoint, as described in Section 5.2.1. Tables will present all data from the baseline and post-baseline timepoints (including follow-up for Part A for those participants that do not continue to Part B of the study).

The primary analysis will be an MMRM (as described in Section 5.2.3) applied to the change from baseline at Weeks 1, 2, 3, 4, 5 and 6, that will be used to estimate the treatment effect related to the primary Estimand 1 (as described in Section 2.1.1).

The following results from the above primary analysis will be plotted:

- Profile plots of the LS Means (including 90% confidence intervals [CIs]) over time, with a separate line for each treatment group
- Profile plots of the LS Mean differences to Placebo (including 90% CIs) over time

Standard SAS output will be provided to support the main statistical summary table for the secondary analysis model, but will not be included in the Clinical Study Report (CSR).

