#### **6.2.2. Change from Baseline for patient reported 7-day recall Cancer-Related Cachexia Symptom Assessment-Fatigue Score, at Weeks 1, 2, 3, 4, 5 and 6**

The Cancer-Related Cachexia Symptom Assessment-Fatigue score will be summarized and analysed in a similar way to the primary endpoint, as described in Section 6.1.1.1.

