## **9. APPENDICES**

## Appendix 1. Statistical Methodology Details

### Example SAS code for MMRM Model:

```
proc mixed data = dataset method=reml;
    class subject treatment time;
    model cfb = treatment base time base*time time*treatment / ddfm=kr residual
outp=resid_out;
    repeated time /subject=subjid type = un;
    lsmeans treatment*time/diff cl alpha=0.1;
    ods output lsmeans=lsmeans_out;
    ods output diffs=diffs_out;
run;
```

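### The appetite and fatigue models may adjust for pain change after randomisation, which can move the estimates off Estimands 1 and 2

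*Protocol*

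**What the plan says.** Protocol 9.4.1.1 lists the fixed terms of the MMRM (baseline, time, treatment and the two interactions with time) and then adds: "Additional terms may be fitted in the model (eg, cancer type, PROMIS-Pain 1a change from baseline score), as appropriate". SAP 5.2.3 repeats this: "Additional terms may be fitted in the model (e.g. cancer type, PROMIS-Pain 1a change from baseline score), as appropriate". Neither document says when an extra term enters, who decides, whether that decision is blinded, or whether the model without it remains primary.

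The model is used for both key efficacy endpoints. In Protocol 9.4.2 the appetite score "will be analyzed using Estimand 1 and an MMRM model", and SAP 6.1.1.1 states: "The primary analysis will be an MMRM (as described in Section 5.2.3) applied to the change from baseline". Fatigue follows in Protocol 9.4.3 under Estimand 2 and the same model, and in SAP 6.2.2 the fatigue "score will be summarized and analysed in a similar way to the primary endpoint".

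The population-level summary of Estimand 1 (Protocol 9.1.1, SAP 2.1.1) begins "Difference in mean change from baseline for the patient reported 7-day recall" and compares PF-06946860 with placebo at Week 4. Estimand 2 has the same form for fatigue. Neither conditions on pain during treatment.

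**The concern.** PROMIS-Pain 1a is completed weekly after dosing, so its change from baseline is measured after randomisation and may itself respond to the drug. Cancer type, the other example in the sentence, is fixed before randomisation and does not raise this problem.

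A model that holds pain change constant estimates the difference between arms at equal pain change. Any part of the drug effect that goes with a change in pain is taken out, or added if the signs are opposed. Protocol 4.2.3 itself expects that pain may influence appetite.

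SAP 5.1 plans no formal hypothesis test, so what is at stake is the Week 4 estimate and its 90% CI. Protocol 9.2 says the study serves internal decisions and possibly the planning of later studies. The choice between two permitted models could also be made with outcomes known: Part A is sponsor-open (Protocol 6.3.2) and unblinded reviews are allowed during the study (Protocol 9.5, SAP 7.1).

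**Working it through.** **The plan's own figures (Protocol 9.2).** Inputs: 20 active and 10 placebo completers, SD 4.2, true effect 4, one-sided 5%.

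- Standard error = 4.2 × sqrt(1/20 + 1/10) = 1.627.
- Power = 79.2% by the normal approximation (77.5% by the t-test on 28 df), against about 80% stated.
- Smallest significant difference = 1.645 × 1.627 = 2.68, against 2.7 stated.
- 90% CI half-width = 1.701 × 1.627 = 2.77.

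**The shift.** Let D be the drug effect on pain change (active minus placebo) and b the within-arm slope of the outcome on pain change. With the total effect held at its true value:

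fitted difference = total effect − (b × D).

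If either b or D is zero, nothing moves.

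**Putting numbers in.** The documents give neither b nor D, so the values below are assumptions: b from -0.3 to -0.7 appetite points per pain point, pain-change SD 2.5, correlation between visits AR(1) 0.7. The formula was checked with a six-visit simulation at 20:10 (10,000 complete-data runs per scenario, unstructured covariance, one common pain slope, 27 df in place of Kenward-Roger; Monte Carlo error about 0.015 to 0.017).

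| D | b | Formula | Simulated |
|---|---|---|---|
| -1 | -0.3 | 3.70 | 3.70 |
| -1 | -0.5 | 3.50 | 3.49 |
| -1 | -0.7 | 3.30 | 3.30 |
| -2 | -0.3 | 3.40 | 3.42 |
| -2 | -0.5 | 3.00 | 2.98 |
| -2 | -0.7 | 2.60 | 2.58 |
| +1 | -0.3 | 4.30 | 4.30 |
| +1 | -0.5 | 4.50 | 4.47 |
| +1 | -0.7 | 4.70 | 4.70 |
| -1 | 0 | 4.00 | 4.00 |
| 0 | -0.5 | 4.00 | 4.01 |

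For D = -0.5 the formula gives 3.85 to 3.65 over the same slopes. The middle case (D = -1, b = -0.5) shifts by 0.5, and 0.5 / 2.77 = 18% of the half-width.

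**Coverage of the Estimand 1 value by the nominal 90% CI.** Without the pain term it is 89 to 91%. With it:

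- D = -1, b = -0.5: 88%.
- D = -1, b = -0.7: 87%.
- D = +1, b = -0.7: 86%.
- D = -2, b = -0.7: 76%.

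Repeat simulations gave 88 to 89%, 87%, 87% and 78% for these four cases.

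**Fatigue.** Higher scores are worse, so assume b from +0.3 to +0.7. With D = -1 the difference moves by +0.3 to +0.7, towards less apparent benefit.

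**The case against.** The strongest reply is that the documents point to a primary model without pain.

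- The named terms will be included, whereas extras only may be.
- The example code in SAP Appendix 1 reads "model cfb = treatment base time base*time time*treatment", with no pain term.
- SAP 6.3.2 plots MMRM residuals against pain change, which makes most sense if pain is not already in the model.
- Protocol 4.2.3 and 8.1.1.3 describe the pain data as exploratory, and a tertiary objective on pain with appetite and fatigue gives a pain-adjusted model a natural home.
- SAP 5.2.3 is a general-methods section that also serves body weight and unbound GDF-15.

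No passage suggests that the drug changes pain. In moderate scenarios the shift is small against the width of the interval. The simulation used complete data, although the plan assumes 25% discontinuation and censors data.

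Much of this stands. The default probably is pain-free, all the sizes are hypothetical, and the worst coverage needs a 2-point effect on pain together with the steepest slope assumed.

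It does not remove the permission. No passage confines the term to an exploratory model. The clauses requiring an amendment for major changes to the primary analysis (Protocol 9, SAP 2) may not catch a term that the protocol already allows. The justification clause in SAP 6.1.1.1 concerns departures from the planned analysis prompted by outliers or non-normality. For Estimand 3, by contrast, SAP 2.1.3 ties the choice to a blinded review before database lock; the added model terms have no such safeguard.

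**Conclusion.** The point holds. Both documents expressly permit a post-randomisation covariate in the models for Estimands 1 and 2, and neither gives a rule for its use. That is certain from the text. The consequence is conditional: the estimate departs from its estimand only if the term is fitted, the drug affects pain, and pain is related to the outcome within arms.

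Under the assumed values, a true appetite effect of 4 would be estimated at anything from about 2.6 (pain lowered by 2) to 4.7 (pain raised by 1), with a modest loss of coverage in most cases. The direction depends on the signs of the two unknowns, so the adjustment cannot be taken to be conservative. The change should be made: the permission bears on the primary estimate and costs almost nothing to remove.

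**What to change.** In SAP 5.2.3, and in Protocol 9.4.1.1 at the next amendment, delete PROMIS-Pain 1a change from baseline from the permitted terms, or state that the models for Estimands 1 and 2 contain only pre-randomisation covariates. Keep pain change for the SAP 6.3.2 plots or for a model labelled exploratory. This costs one sentence and no data, visits or participants.

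If adjustment for pain is wanted, prespecify the Day 1 PROMIS-Pain 1a score, which the Schedule of Activities already collects, before any unblinded review. That option has a small price. In simulation at the protocol's one-sided 5% level, adding it to a model with baseline appetite (taken as uninformative) lowers power from 76.0% to 74.6% if baseline pain explains nothing. It breaks even at about 4% of within-arm Week 4 variance, and at 10% power rises from 76.1% to 78.5%.
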